1.7 Table of endpoints/outcomes

Objectives	Outcome Measures	Timepoint of evaluation of this outcome measure
Primary Objective To assess the feasibility of the present trial in terms of participant retention	Participant retention \geq 70%	End of tDCS sessions (visit 21)
Secondary Objective To assess the acceptability of the intervention	Positive endorsement of tDCS sessions as measured by an acceptability questionnaire	End of tDCS sessions (visit 21)

2 TRIAL DESIGN

The trial is a pilot, open-label, single arm trial to determine the feasibility and acceptability of tDCS for major depression within a community-based setting.

3 PARTICIPANT ELIGIBILITY CRITERIA

3.1 Inclusion criteria

- participants capable of giving informed consent
- male and female
- minimum of 18 years of age
- diagnosis of major depressive disorder based on DSM-5 criteria, with a current depressive episode of at least a moderate severity
- diagnosis will be determined by the Mini-International Neuropsychiatric Interview
- severity will be assessed using the HRSD with a minimum score of 16 indicating at least a moderate severity of symptoms
- taking antidepressant medication or being involved in psychological therapy.

3.2 Exclusion criteria

- treatment resistant depression as defined by a poor clinical response to 2 or more antidepressant trials
- any concurrent psychiatric disorder, including bipolar disorder or any psychotic disorder
- having a significant risk of suicide
- exclusion criteria for tDCS, including having a scalp or skin condition (e.g. psoriasis or eczema); if contact with the scalp is not possible; having metallic implants, including intracranial electrodes, surgical clips, shrapnel or a pacemaker
- history of epilepsy
- history of a seizure which resulted in a loss of consciousness
- neurological disorder or history of migraines

4 TRIAL PROCEDURES

The Schedule of Events is presented in table format in Appendix 2.

4.1 Recruitment

Recruitment will be from primary care, consulting psychiatrists, print and social media advertisements.

4.1.1 Participant identification

Potential participants will be referred by their GPs and psychiatrists as well as recruited by publicity, leaflets and websites.

Only a member of the patient's existing clinical care team will have access to patient records without explicit consent in order to identify potential participants, to check whether they meet the inclusion criteria and to make the initial approach to patients.

Participants will be identified by their responsible physician or will be identified by self-referral. All participants will be required to be under the care of a GP for study participation.

4.1.2 Screening

The screen assessment requires a DSM-5 diagnosis of major depressive disorder by a MINI interview assessment and a minimum score of 16 on the HRSD. The maximum duration between screening and recruitment is 20 days.

4.1.3 Payment

Participants will be reimbursed for reasonable travel expenses up to £15 as a voucher per visit. Participants will be reimbursed a £5 voucher for each 30 minute tDCS session for their time, which will be a total of £105 in vouchers for 21 sessions, and will be reimbursed a £10 voucher for each of the optional EEG sessions (visits 1, 10, 21), which will be a total of £30 in vouchers for 3 EEG sessions.

4.2 Consent

The Chief Investigator (PI) retains overall responsibility for the conduct of research which includes the taking of informed consent of participants at their site. The PI will ensure that any person delegated responsibility to participate in the informed consent process is duly authorised, trained and competent to participate according to the ethically approved protocol, principles of Good Clinical Practice (GCP) and Declaration of Helsinki.

Informed consent will be obtained prior to the participant undergoing procedures that are specifically for the purposes of the trial and are out-with standard routine care at the participating site.

The right of a participant to refuse participation without giving reasons will be respected.

The participant will remain free to withdraw at any time from the trial without giving reasons and without prejudicing his/her further treatment and will be provided with a contact point where he/she may obtain further information about the trial. Data and samples collected up to the point of withdrawal will only be used after withdrawal if the participant has consented for this. Any intention to utilise such data is outlined in the consent literature. Where a participant is required to re-consent or new information is required to be provided to a participant, the PI will ensure this is done in a timely manner.

The PI takes responsibility for ensuring that all vulnerable participants are protected and participate voluntarily in an environment free from coercion or undue influence.

The potential participant will discuss with an individual knowledgeable about the research about the nature and objectives of the trial and possible risks associated with their participation. The potential participant will have the opportunity to ask questions.

The written material (information leaflet and consent document) is approved by the REC and is in compliance with GCP, local regulatory requirements and legal requirements

All participants will be capable of giving consent for themselves:

- understand the purpose and nature of the research
- understand what the research involves, its benefits (or lack of benefits), risks and burdens
- understand the alternatives to taking part
- be able to retain the information long enough to make an effective decision.
- be able to make a free choice
- be capable of making this particular decision at the time it needs to be made

4.2.1 Additional consent provisions for collection and use of participant data and biological specimens in ancillary studies, if applicable: N/A

4.3 The randomisation scheme: N/A

4.3.1 Method of implementing the randomisation/allocation sequence: N/A

4.4 Blinding: N/A

4.5 Emergency Unblinding: N/A

4.6 Baseline data

The baseline data consist of: HRSD, PHQ-9, HAMA, YMRS, SDS, tDCS AEQ, Acceptability questionnaire, EEG (optional) (Appendix 2).

4.7 Trial assessments

Trial assessments are described in Appendix 2.

4.8 Long term follow-up assessments

Long term follow-up assessments will be acquired at 3 months and at 6 months following the final treatment visit (Appendix 2).

Participants who do not respond to repeated attempts at contact will be identified as 'lost to follow-up'.

4.9 Qualitative assessments

At the final tDCS session, participants will complete the acceptability questionnaire and provide feedback on their experience of the study.

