1.2 Secondary objective

The secondary objective is to assess the acceptability of the tDCS sessions.

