1.5 Secondary endpoints/outcomes

The hypothesis is that participants will positively endorse the tDCS sessions at the end of the trial as measured by an acceptability questionnaire scale.

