5.11 Assessment of compliance with treatment

The tDCS device records the duration of each session, and there is an automatic shut-off to prevent unsafe use. The equipment will be programmed to provide only the type of stimulation, intensity and session length that are specified in the protocol. The placement is determined by the location of the electrodes which are fitted to specific locations in the cap. The research assistant will be present at each session, in person or via video link, in order to aid in the initial positioning and to monitor for any adverse events.

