7.3.3 Secondary outcome analysis

The secondary outcome analyses will be the percentage of participants rating the intervention as acceptable at the end of the 6 week course of tDCS. The acceptability scale consists of the question 'How acceptable did you find the tDCS sessions?' with responses ranging from 'Very unacceptable' to 'Very acceptable' on a 7-point anchored Likert scale with the acceptable ratings being from rating 5-7.

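### The only secondary endpoint, a single acceptability rating, is collected at a staff-attended session with no stated provision for private completion, so courtesy bias may inflate it

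*Combined protocol and SAP*

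**What the plan says.** Section 1.2 gives one secondary objective: "The secondary objective is to assess the acceptability of the tDCS sessions". Section 1.5 states the matching hypothesis, that "participants will positively endorse the tDCS sessions at the end of the trial as measured by an acceptability questionnaire scale", without a numeric target. The table in 1.7 places the measurement at visit 21.

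Section 7.3.3 defines the analysis as "the percentage of participants rating the intervention as acceptable at the end of the 6 week course of tDCS". The instrument is one question, "How acceptable did you find the tDCS sessions", answered "on a 7-point anchored Likert scale with the acceptable ratings being from rating 5-7".

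Section 4.9 fixes when the rating is taken: "At the final tDCS session, participants will complete the acceptability questionnaire and provide feedback on their experience of the study". On staffing, section 5.11 says: "The research assistant will be present at each session, in person or via video link". It gives the reasons as help with initial positioning and monitoring for adverse events. Section 5.6 adds that the assistant supervises but is to be discreet and not interact with the participant.

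The supplied text does not say:
- who hands out or collects the form;
- whether it is filled in during or after stimulation;
- whether it is on paper or electronic;
- whether staff see the answer.

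Sections 4, 4.6 and 4.7 refer to Appendix 2 for the schedule and assessments. That appendix is not in the supplied text.

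**The concern.** A subjective rating of the study sessions, given where the supervising staff may see or hear it, is open to courtesy bias. The plausible direction is upward.

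Three features of the plan leave the endpoint exposed:
- **Cut-off.** The lowest acceptable rating, 5, is one step above the scale midpoint of 4. A neutral participant who is only slightly polite changes category.
- **Design.** Section 2 describes an open-label, single-arm trial. No second arm shares the bias and lets it cancel.
- **Reporting.** With no success threshold, the raw percentage is the whole result, so any inflation passes straight into the conclusion.

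Acceptability is half of the aim stated in section 1, and section 5.3 says the findings will be used to design a multi-site sham-controlled trial. An over-favourable figure could carry into that design.

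**Working it through.** **1. The plan's own figures.** Section 7.1 enrols 30 to obtain 24 completers at 20% attrition: 24 / (1 − 0.20) = 30, which reproduces. Section 5.6 gives 5 × 3 + 2 × 3 = 21 sessions, which agrees with visit 21 in section 1.7. The documents give no power calculation or target for acceptability, so there is nothing further to reproduce for this endpoint.

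**2. The sections side by side.**
- 4.9: the form is completed at the final session.
- 5.6 and 5.11: a research assistant supervises and attends each session, on site or by video.
- 7.3.3: the item is subjective and is dichotomised at 5.
- No supplied section separates the assistant from the completion of the form.

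A site can therefore follow the plan to the letter and take the rating with the supervisor in the room or on the link. A site that takes it privately also complies. The plan permits the exposed method but does not require it.

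**3. Sensitivity of the endpoint.** The documents do not allow the bias to be estimated. What can be shown is how far the percentage moves if k raters cross from 4 to 5. The change is 100 × k / n, with n = 24 (planned completers, section 7.1) or n = 30 (all enrolled, in line with the intention-to-treat statement in section 7.7). The values of k are assumptions.

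| k (assumed) | n = 24 | n = 30 |
|---|---|---|
| 1 | 4.2 points | 3.3 points |
| 2 | 8.3 points | 6.7 points |
| 3 | 12.5 points | 10.0 points |
| 5 | 20.8 points | 16.7 points |

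As an example, assume 15 of 24 would privately rate the sessions acceptable: 15/24 = 62.5%. One shift gives 16/24 = 66.7%; three give 18/24 = 75.0%. The starting value of 15 is also an assumption.

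**4. Comparison with sampling error.** For an assumed 18/24, the exact (Clopper-Pearson) 95% limits are the 2.5% quantile of Beta(18, 7) and the 97.5% quantile of Beta(19, 6), that is 53.3% and 90.2%. The interval is 90.2 − 53.3 = 36.9 points wide, so a few shifts are small beside chance variation. A systematic shift, however, is not reflected in the interval and does not shrink with more participants.

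**The case against.** The strongest reply is that the harm is inferred. A reader might conclude that the form is filled in during stimulation, in front of the person who delivered up to 21 sessions, and that this certainly pushes the rating up. The documents do not support that reading:
- Section 4.9 says only that completion is at the final session. Presence of the assistant at that moment comes from joining it to 5.6 and 5.11.
- Section 5.6 has participants taught to give the treatment to themselves, and refers to assistants in the plural. No section ties one assistant to one participant. The item asks about the sessions, not about the assistant.
- The assistant is told to be discreet and not to interact, which is a partial mitigation.
- Nothing in the documents shows the direction or size of any effect, or that it differs between in-person and video participants.
- Appendix 2 may already describe how the form is given.

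Two further replies concern weight. No threshold exists to be crossed, and the primary endpoint, retention, is unaffected. Moving the form outside the session could also lose some forms. Section 7.8 imputes missing data by last observation carried forward and section 4.6 lists the acceptability questionnaire at baseline, so a lost form could be replaced by a baseline rating.

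All of this stands as a limit on how strongly the point may be put. It does not remove the gap: discretion during a session is not privacy for a rating, and the supplied text offers no other safeguard. The risk of lost forms is a reason to keep completion within the visit, not to leave the method open.

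**Conclusion.** The point holds as a risk, not as a demonstrated bias. The sole secondary endpoint is a single subjective item collected at a staff-attended session, with no written provision for private completion in the supplied text. Courtesy may inflate it, and the design has no comparator to offset that.

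The size is unknown. Each crossing of the cut-off is worth 4.2 points with 24 raters or 3.3 with 30; how many would cross cannot be derived from the documents.

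The conclusion assumes that Appendix 2 does not already specify private completion; if it does, a cross-reference in 4.9 is enough. The matter does not threaten the trial, but it is worth changing because a less bias-prone method costs almost nothing.

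**What to change.** Add to section 4.9:
- After stimulation ends at visit 21, and before the visit closes, the participant completes the acceptability item alone, with the research assistant out of the room or off the video link.
- All participants use the same mode, either an online form or a sealed form, identified by study number.
- Participants are told beforehand that the staff who supervised their sessions will not see individual answers.

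Add to section 7.8 that a missing end-of-course acceptability form is reported as missing and is not filled with the baseline acceptability rating, which precedes the sessions being rated.

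The cost is a few sentences and a simple form, with no extra visit or participants. Someone other than the supervising assistant must receive the answers; an online form largely takes care of this. A small risk of unreturned forms remains, limited by completion within the visit.

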4.10 Withdrawal criteria

Participants will be withdrawn from the trial if they do not comply with the intervention, namely if they are unable to have a minimum of 50% of the tDCS session (10 out of 21 sessions), or if they develop serious adverse effects from any part of the study. Recording of the reasons for withdrawal will be made. Their GP will be informed about their withdrawal, and there will have a telephone follow up at 1 month following their withdrawal.

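### Section 4.10 treats stopping tDCS as leaving the trial, with no stated visit 21 assessment, and the retention formula in 7.3.2 read literally counts everyone who starts as retained

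*Combined protocol and SAP*

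**What the plan says.** **Withdrawal.** Section 4.10 reads "Participants will be withdrawn from the trial if they do not comply with the intervention". It explains non-compliance as being unable to have at least half of the sessions, glossed as 10 of 21, and adds serious adverse effects from any part of the study as a second trigger. Reasons are recorded, the GP is told, and "there will have a telephone follow up at 1 month following their withdrawal". No supplied section separates stopping tDCS from leaving the study.

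**Assessments and analysis.** Section 1.7 evaluates both retention and acceptability at "End of tDCS sessions (visit 21". Section 4.9 collects the acceptability questionnaire at the last tDCS session. Section 4.8 says "Long term follow-up assessments will be acquired at 3 months and at 6 months following the final treatment visit". Section 7.7 puts all participants in an intention-to-treat analysis, and 7.8 fills any missing value by last observation carried forward. The baseline list in 4.6 is "HRSD, PHQ-9, HAMA, YMRS, SDS, tDCS AEQ, Acceptability questionnaire, EEG (optional", so the acceptability questionnaire is among the baseline measures.

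**Retention.** Section 1.4 sets the target at 70% or more. The only formula is in 7.3.2: enrolled participants who have not dropped out *before* the six-week course, divided by all enrolled. Section 7.1 plans on 24 of 30 completing the course.

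**The concern.** People who cannot tolerate tDCS, or who have a serious effect from it, are the ones whose view of acceptability matters most. If stopping treatment ends trial participation, their visit 21 rating is not provided for, and the analysis of all participants rests on a filled-in value. For acceptability that value may be the baseline one, given before any session. The scored question in 7.3.3 asks in the past tense how acceptable the sessions were, which a baseline rating cannot answer.

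Retention is the primary outcome, and 5.3 says the findings will be used to design a sham-controlled trial. A formula that counts every starter as retained would tell that trial nothing about staying in. Section 4.10 also merges two quantities that the next trial needs separately: how many sessions people manage, and whether they remain willing to be assessed.

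**Working it through.** **1. The plan's own figures.** Section 7.1: 24 / (1 − 0.20) = 30, which reproduces. Section 5.6: 5 × 3 + 2 × 3 = 21 sessions, which agrees. Section 1.4: 0.70 × 30 = 21 participants.

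**2. The session floor.** 10/21 = 47.6% and 11/21 = 52.4%. Someone with exactly 10 sessions meets the count in 4.10 but not the 50% label.

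**3. How many stop before completing 10 sessions.** Sessions delivered by the end of weeks 1 to 6 are 5, 10, 15, 17, 19 and 21, so the tenth falls at the end of week 2. The documents give no timing of drop-out. Assume a constant hazard and completion c = 0.80, from 7.1:

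- hazard per week: 30 × (1 − 0.80^(2/6)) = 2.15
- hazard per session: 30 × (1 − 0.80^(10/21)) = 3.02

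That is about 2 to 3 of 30. Without the assumption, the range is 0 to 6, since 20% of 30 is 6. Serious adverse effects after session 10 also trigger 4.10; no rate is given, but at planned attrition they fall within the same 0 to 6.

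**4. How much a change could recover.** Some early stoppers would leave whatever 4.10 says. Let f be the share willing to stay, assumed to be 0.25 to 1:

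- low: 0.25 × 2.15 = 0.54 people; 0.54/30 = 1.8 points
- high: 1 × 3.02 = 3.02 people; 3.02/30 = 10.1 points

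This is about 0.5 to 3 people, or 2 to 10 points of the acceptability percentage.

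**5. What the handling of missing ratings can do.** Suppose 20 of 24 completers rate 5 to 7 (assumed) and 6 have no visit 21 rating:

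| Handling of the 6 | Acceptability |
|---|---|
| Left out | 20/24 = 83.3% |
| Counted as not acceptable | 20/30 = 66.7% |
| All carried forward as acceptable | 26/30 = 86.7% |

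**6. Retention under the literal formula.** If all 30 start, 7.3.2 read literally gives 30/30 = 100%. Course completion at the planned rate gives 24/30 = 80%. If only 18 complete (assumed), the two figures are 100% and 60%, on opposite sides of the target. When everyone starts, the literal count cannot miss 70%, so the two disagree whenever fewer than 21 complete. The binomial probability of that with n = 30 is 6.1% if true completion is 80%, 19.7% at 75% and 41.1% at 70%.

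**The case against.** **Visit 21 data may not be lost.** A reader might infer that 4.10 removes these data. The documents do not go that far: 4.10 does not forbid an end assessment, and Appendix 2, which holds the schedule, is not in the supplied text. What stands is that no supplied section provides for the assessment. The withdrawal trigger may also come late. Being unable to have 10 sessions is certain only after 12 are missed, which is session slot 12 at the earliest and slot 21 for someone who stops after 9. On that reading 4.10 does not exclude a person at the moment they stop.

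**There are not four rival retention counts.** Only 7.3.2 is a formula. Section 4.10 is a withdrawal rule, 1.7 a timepoint and 7.1 a planning figure, and 1.7 and 7.1 are compatible. It is tempting to treat not being withdrawn under 4.10 as another retention count and compute how often it and completion straddle 70%, but no section calls that retention. *Before* in 7.3.2 is plausibly a slip for *before the end of*. That is likely, but the slip sits in the primary outcome formula and should be corrected.

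**Other losses do not follow.** Section 4.2 says "Data and samples collected up to the point of withdrawal will only be used after withdrawal if the participant has consented for this", which might suggest that earlier data are lost too. The same section says that any intended use is set out in the consent literature, which is not available here. Nor are adverse-event data shown to be lost: 6.9 records events for 3 months after the last tDCS and makes no exception for withdrawn participants. Retention itself can still be computed for withdrawn people, because their status is known.

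**Conclusion.** The point holds in a narrow form and merits consideration. As written, 4.10 equates stopping tDCS with leaving the trial, and the supplied text leaves visit 21 unprovided for in those who stop; 7.8 could then put a pre-treatment rating into the secondary outcome. The effect is modest: about 2 to 10 points of acceptability at planned attrition, resting on an assumed constant hazard and an assumed 25% to 100% of early stoppers willing to stay. The retention wording matters more if taken literally (close to 100% against 80%) and not at all if the sponsor already reads it as the end of the course. The mismatch between 50% and 10 of 21 affects only a person with exactly 10 sessions. Appendix 2 could settle the visit question. Nothing here changes the sample size of 30.

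**What to change.** **Section 4.10.** Replace the first sentence with: *tDCS is stopped for serious adverse effects. Stopping tDCS, or having fewer than 10 of 21 sessions, is recorded with its reason and is not withdrawal from the trial; the participant is asked to complete the visit 21 assessment (end of week 6) and the 3- and 6-month assessments. Withdrawal is the participant's own choice.* This also drops the 50% label. Keep the GP notice and the 1-month call. No further stopping rules are needed.

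**Section 7.3.2.** Make the cut-off *before the end of the six-week course (visit 21)*. State one rule: retained means assessed at visit 21, over all enrolled. If the sponsor wants a session floor in the primary outcome, add it here. Report the numbers with at least 10 and with all 21 sessions beside it; the latter is the figure to compare with the 24 in 7.1.

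**Section 7.8.** Do not carry a baseline acceptability rating forward. Count a missing visit 21 rating as not acceptable, and show the observed ratings beside it.

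**Cost.** Three wording changes, a line in the consent form, and up to 3 assessments for each early stopper who stays: 2 to 3 people × 3 = 6 to 9, at most 6 × 3 = 18. Section 4.1.3 allows "reasonable travel expenses up to £15 as a voucher per visit", so travel is at most £90 to £135, or £270 at the extreme. Trained-rater time for the HRSD, HAMA and YMRS comes on top and cannot be priced from the documents. The main downside is that attending visit 21 is easier to achieve than completing the course, which is why the session counts must be shown with it.

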5.4 Drug storage and supply (if applicable): N/A

5.5 Preparation and labelling of Investigational Medicinal Product (if applicable): N/A

5.6 Dosage schedules:

The electrodes will be placed in a bifrontal montage, in which the anode is placed over the left dorsolateral prefrontal cortex (DLPFC) and the cathode is placed over the right DLPFC. This is

[figure not shown]
Figure 1. StarStim tDCS device

Figure 2. Flow tDCS device

Figure 3. Soterix tDCS device

equivalent to the EEG positions at F3 and F4, respectively. The stimulation will be 2 mA, and the electrode area is 35 cm².

Participants will receive a 6-week course of active tDCS treatment, consisting of 5 sessions per week for the first 3 weeks followed by 2 sessions per week for 3 weeks, for a total of 21 tDCS sessions. The duration of each session is 30 minutes.

The tDCS parameters are based on meta-analyses (Meron et al., 2015; Brunoni et al., 2016; Mutz et al., 2018) which demonstrate that treatment effects are most evident at 2 mA current of 30 minute stimulus duration for 21 sessions for participants with recurrent major depression.

During the first session, participants will be taught by the study team how to fit the cap and deliver the tDCS treatment to themselves. During each session, the participant will be seated comfortably, and the research assistant will provide a discreet presence without interacting with the participant. The research assistant will supervise sessions either in person or via video link. Research assistants and participants will wear appropriate PPE during any sessions conducted at the study site or where the research assistant is present in person.

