7.3.2 Primary outcome analysis

The primary outcome analysis is participant retention which will be measured by the number of enrolled participants who do not drop out before the 6 week course of tDCS, divided by the total number of enrolled participants, expressed as a percentage.

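### The withdrawal threshold in section 4.10 is given as at least 50% and as 10 of 21 sessions, but 10 of 21 is 47.6% and a 50% minimum needs 11

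*Combined protocol and SAP*

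**What the plan says.** Section 4.10 (Withdrawal criteria) sets one numerical rule for non-compliance. A participant is withdrawn if "unable to have a minimum of 50% of the tDCS session (10 out of 21 sessions". The same section sets out what follows: the reason is recorded, and "Their GP will be informed about their withdrawal, and there will have a telephone follow up at 1 month following their withdrawal".

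Three other places fix the number of sessions:

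- Section 5.6 (Dosage schedules) describes "5 sessions per week for the first 3 weeks followed by 2 sessions per week for 3 weeks", "for a total of 21 tDCS sessions".
- Section 4.1.3 (Payment) gives a £5 voucher per session, "which will be a total of £105 in vouchers for 21 sessions".
- Section 1.7 (Table of endpoints/outcomes) times the primary and secondary outcomes at "End of tDCS sessions (visit 21".

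The plan gives no rule for rounding and does not say whether the percentage or the count governs. It does not say how a participant with exactly 10 sessions is to be handled.

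**The concern.** The bracketed count follows directly on the word minimum, so it reads as the same threshold put into sessions. Ten sessions out of 21 is less than half, so it cannot satisfy a minimum of one half. A member of staff who applies the percentage would withdraw a participant with 10 sessions; one who applies the count would keep that participant. Both would be following section 4.10.

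What is at stake is consistent conduct. The rule is applied to one person at a time and leads to definite actions. It also belongs to a feasibility study whose findings, according to section 5.3, will be used to design a multi-site sham-controlled trial, so an unclear rule could be carried forward.

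**Working it through.** **Inputs.** Session schedule and total: section 5.6. Voucher value and total: section 4.1.3. Final visit number: section 1.7. Threshold in both forms: section 4.10.

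**Step 1: the denominator.**
- From the schedule: 5 × 3 + 2 × 3 = 15 + 6 = 21.
- From the payments: £105 / £5 = 21.
- From the endpoint table: the last session is visit 21.

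All three agree. A total of 20 would make 10 sessions exactly 50%, but nothing in the plan supports 20.

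**Step 2: try to reproduce the plan's count.** The threshold is the smallest whole number k with k/21 ≥ 0.50. Since 0.50 × 21 = 10.5, k = 11. The plan's figure, "10 out of 21 sessions", is obtained only by rounding 10.5 down, which gives a value below the stated minimum:
- 10/21 = 47.6%
- 11/21 = 52.4%

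**Step 3: where the two forms part.** The percentage form withdraws if k/21 < 0.50, that is, if k ≤ 10. The count form, with 10 as the minimum, withdraws if k < 10.

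| Sessions | Share of 21 | Percentage form | Count form (10 is the minimum) |
|---|---|---|---|
| 9 | 42.9% | withdraw | withdraw |
| 10 | 47.6% | withdraw | keep |
| 11 | 52.4% | keep | keep |

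Below 9 both forms withdraw, and above 11 both keep. Of the 22 possible counts (0 to 21), one is classified differently. That is a tally of possible values, not a probability: the plan gives no distribution of attendance.

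**Step 4: the same rule in missed sessions.** The criterion concerns being unable to reach the minimum, so staff may in practice count absences. With a minimum of 11, a participant can miss 21 − 11 = 10 sessions, and the 11th absence puts the minimum out of reach. With a minimum of 10, a participant can miss 21 − 10 = 11, and it is the 12th absence. The two forms differ by one absence.

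**Step 5: the alternative reading.** If the bracket is taken as the level that fails, the count form withdraws if k ≤ 10. This is identical to the percentage form, and the number of conflicting counts is 0 of 22.

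**Step 6: reach into the analysis.** Section 7.3.2 defines retention as the "number of enrolled participants who do not drop out before the 6 week course of tDCS, divided by the total number of enrolled participants". It does not say whether a withdrawal under 4.10 counts as dropping out. If it did, which is an assumption, each affected participant would move retention by 1/30 = 3.3 percentage points with the 30 enrolled in section 7.1. The sample size does not use the threshold: 24 / (1 − 0.20) = 30.

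**The case against.** The strongest reply is that no one can attend 10.5 sessions, so any whole-number version of 50% must move off 50%, and 10 and 11 are equally far from it. On this view the percentage is the principle and the bracket is the working rule. Staff count sessions and have been given a number. This explains how the text may have arisen, but it does not remove the conflict: a minimum is not met by rounding down to a value below it, and nothing in the plan says that the count prevails.

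A second reply is that the bracket may give the failing level, in which case there is no conflict at all. That reading is possible and is shown in step 5. It is the less natural one, because the bracket directly follows the stated minimum. That both readings remain open is itself a defect in a rule meant to be applied without discretion.

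A third reply is that the reach is very small. This stands. Only a participant with exactly 10 sessions is affected, in a pilot of 30, and there may be none. Section 7.7 includes all participants in the intention-to-treat analysis, so the boundary does not decide membership of that set. No safety harm is identified.

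It can also be said that nothing in the plan ranks the percentage above the count, so a preference for 11 is a choice. That is fair, and the sponsor should settle which was meant.

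**Conclusion.** The concern holds, as a minor one. The count in section 4.10 is not the smallest number of sessions that meets the stated minimum: that number is 11, and the plan gives 10. The arithmetic is certain, given a total of 21, which three sections confirm. That the two forms conflict in use rests on reading the bracket as the minimum; on that reading the conflict is confined to exactly 10 sessions.

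The consequence is for trial conduct: whether that participant is withdrawn, and whether the GP is informed and the one-month call made. No effect is shown on the 70% retention endpoint, the analysis sets or the sample size. The 3.3-point figure in step 6 depends on an unstated convention, and the conclusion does not rest on it.

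**What to change.** State one whole-number rule in section 4.10. There are two options:

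- **Default, which keeps the stated 50% minimum:** *withdrawn if fewer than 11 of 21 sessions can be completed*.
- **If the sponsor intended 10 as the minimum:** *withdrawn if fewer than 10 of 21 sessions (about 48%) can be completed*.

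Either wording settles the case of exactly 10 sessions. The cost is a one-line correction. It needs no extra data and leaves the endpoints, sample size and analysis sets as they are.
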